Sensitivity analysis: impact of exogenous FVIII product use in the efficacy evaluation period (EEP) on ABR	--	Not planned	
The following sensitivity analyses will be performed by counting exogenous FVIII product use in EEP as bleeding events:
 
 #1: count each one-time FVIII prophylaxis use in EEP as one bleed #2: count each one-time or routine FVIII prophylaxis use in EEP as one bleed 
#3: count each one-time or routine FVIII prophylaxis use and each surgery/procedure that had FVIII use in EEP as one bleed

Additional sensitivity analysis: impact of IS on ABR and FVIII activity	--	Not planned	
The following sensitivity analyses will be performed in subjects who have been off IS for at least 12 months
 
 Repeat the primary analysis of ABR (ABR

			change from baseline) in this subgroup Repeat the primary analysis of FVIII activity (FVIII activity change from baseline at Week 104) in this subgroup
Washout period between the last dose of FVIII prophylaxis following gene therapy and the start of EEP	No washout period	3 days	Based on the half-life of the original FVIII prophylaxis product: 
 • 3 days for standard half-life or plasma-derived products • 5 days for extended half-life
Definition of AEs/SAEs related to IS	--	All AEs/SAEs during or within 2 weeks' post-IS use	All AEs/SAEs following IS use up to each subject's last visit for the analysis
IS (CS or AIS) therapy to be included in the analysis	--	Systemic IS (CS or AIS) indicated for ALT elevation of any duration, or indicated for other purposes with a duration of at least 4 weeks	Systemic IS (CS or AIS) indicated for any purpose of any duration
Definition of an IS course (cycle)	--	The start of an IS use through the end of taper or increase in IS dose for ≥ 2 consecutive weeks preceded by at least 2 decreases in IS dose, whichever occurs earlier	The time period between the first day of starting an IS therapy to the last day of IS use. Any increase in the dose of IS will be considered as a new cycle of IS therapy with the first day of increase of IS dose constituting as the start day of a new cycle.

Comment(s)/ Recommendation(s):

This NTF serves as a bridging document between the analysis methods in the 270-301 protocol (version 7.0, 15 July 2021; US-specific), the 2-year analysis SAP (version 2.0, 13 December 2021) and the 2-year 270-301 CSR.

DocuSigned by:
PI
 Signer Name: **PI**

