13.1 Efficacy Evaluation Periods

To avoid breakthrough bleeding, subjects only discontinued exogenous prophylactic FVIII replacement therapy after 4 weeks following infusion of BMN 270. Four weeks represents the time by which endogenous production of FVIII following gene transfer is expected to be efficacious, based on earlier results. For the purpose of primary data analysis, the efficacy evaluation period for

- Efficacy endpoints such as ABR, number of treated bleeds, annualized FVIII utilization, annualized FVIII infusions and PROs: will be defined as starting from Week 5 post-BMN 270 dosing (Study Day 33) or 3 days after the end of FVIII prophylaxis, whichever is later, until subjects complete the study, reach the last visit by data cutoff for the analysis, or withdraw from the study (ETV), whichever is the earliest.
- Efficacy endpoint of FVIII activity based on chromogenic substrate assay: will be defined as starting from Week 5 post-BMN 270 dosing (Study Day 33) until subjects complete the study, reach the last visit by data cutoff for the analysis, withdraw from the study (ETV) (FVIII activities post withdrawal will be imputed to be 0 IU/dL through the data cutoff date for the analysis), or resume routine FVIII prophylaxis (should that occur) (Restart of FVIII prophylaxis is defined as the first usual FVIII prophylaxis administered at least once a week for ≥ 4 consecutive weeks), whichever is the earliest.

Study 270-301 Statistical Analysis Plan

- Efficacy endpoint of FVIII activity based on one-stage assay: will be defined as starting from Week 5 post-BMN 270 dosing (Study Day 33) until subjects complete the study, reach the last visit by data cutoff for the analysis, withdraw from the study (ETV) (FVIII activities post withdrawal will be imputed to be 0 IU/dL through the data cutoff date for the analysis), or resume routine FVIII prophylaxis or start emicizumab prophylaxis (should that occur) (Start of emicizumab prophylaxis is defined as the first emicizumab injection among 2 or more emicizumab injections administered within 31 days), whichever is the earliest.

For the purpose of supportive data analyses, the efficacy evaluation period for

- Efficacy endpoint of FVIII activity: will be defined as from BMN 270 infusion to until subjects complete the study, reach the last visit by data cut-off for the analysis, or withdraw from the study (ETV), whichever is the earliest.

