- Efficacy endpoints such as ABR, number of treated bleeds, annualized FVIII utilization, annualized FVIII infusions: will be some of the efficacy evaluation periods listed in [Table 13.1.1](#). In addition, descriptive summary will be provided in Weeks 1-4 and Week 1-end of FVIII prophylaxis (defined as end of week 4 post-BMN 270 infusion or 2 days after end of FVIII prophylaxis, whichever is later).

Time to discontinuation of FVIII prophylaxis post-BMN 270 infusion and duration of efficacy evaluation period for primary analysis of primary and secondary efficacy endpoints will be summarized.

[figure not shown]

Table 13.1.1: Efficacy Evaluation Periods for Analyses of Primary and Second-Ranked Secondary Efficacy Endpoints

Efficacy Evaluation Period	Start Point	End Point	Analysis
Post-FVIII prophylaxis period	Start of Week 5 post-BMN 270 infusion or 3 days after end of FVIII prophylaxis, whichever is later	Last visit by data cut-off	Primary, t-test
Post-FVIII prophylaxis – week 104	Start of Week 5 post-BMN 270 infusion or 3 days after end of FVIII prophylaxis, whichever is later	Last visit by data cut-off or end of Week 104 post-BMN 270 infusion, whichever is earlier	Supportive, t-test
Post-FVIII prophylaxis – restart of prophylactic treatment up to Week 104	Start of Week 5 post-BMN 270 infusion or 3 days after end of FVIII prophylaxis, whichever is later	Last visit by data cut-off, end of Week 104 post-BMN 270 infusion or 1 day before restart of prophylactic treatment, whichever is earlier	Supportive, t-test
Post-FVIII prophylaxis – restart of prophylactic treatment up to last visit	Start of Week 5 post-BMN 270 infusion or 3 days after end of FVIII prophylaxis, whichever is later	Last visit by data cut-off or 1 day before restart of prophylactic treatment, whichever is earlier	Supportive, t-test

Note: end of FVIII prophylaxis is defined as last usual FVIII prophylaxis not followed by another usual FVIII prophylaxis for at least 28 days.

Restart of prophylactic treatment means restart of FVIII or start emicizumab prophylaxis. Restart of FVIII prophylaxis is defined as the first usual FVIII prophylaxis administered at least once a week for ≥ 4 consecutive weeks. Start of emicizumab prophylaxis is defined as the first emicizumab injection among 2 or more emicizumab injections administered within 31 days.

Study 270-301 Statistical Analysis Plan

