13.2.1 Primary Estimand

The estimand formulation for the primary efficacy endpoint is as follows:

Treatment

(BMN 270 gene therapy + rescue therapy) vs. (FVIII prophylaxis + rescue therapy)

The rescue therapy for the BMN 270 gene therapy includes FVIII infusions for different purposes (routine prophylaxis, one-time prophylaxis, treatment for bleeds, and for surgery/procedure) and the emicizumab prophylaxis for hemophilia A.

The rescue therapy for FVIII prophylaxis includes FVIII infusions for other purposes (one-time prophylaxis, treatment for bleeds, and for surgery/procedure).

Population

HIV-negative subjects with severe hemophilia A

Variable (endpoint)

ABR (treated bleeds)

	Study 270-301 Statistical Analysis Plan
---	--

Intercurrent events and strategies

Intercurrent Events		Strategies for Addressing Intercurrent Events				
		Treatment Policy Strategy	Hypothetical Strategies	Composite Variable Strategies	While-on-Treatment Strategies	Principal Stratum Strategies
Death (unrelated to study drug)					✓	
Lost to follow-up					✓	
FVIII infusions	Started routine prophylaxis	✓				
	One-time prophylaxis	✓				
	Treatment for bleeds	✓				
	For surgery/procedure	✓				
	Started emicizumab prophylaxis	✓				

Population-level summary

Mean ABR (treated bleeds) change from baseline

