13.3 Secondary Efficacy Endpoints

The first-ranked secondary efficacy endpoint is:

- The change from baseline (assuming no treatment for severe hemophilia A) in FVIII activity, as measured by chromogenic substrate assay, at Weeks 104 post-BMN 270 infusion

Each subject's FVIII activity level at Week 104 is defined as the median of the values obtained at Week 104 with the window defined in Appendix 20.1. The baseline value will be imputed as 1 IU/dL, since there will be no washout of severe hemophilia A subjects' usual FVIII prophylaxis (in order to avoid increasing the risk of bleeding) prior to BMN 270 infusion. Post-BMN 270 infusion values for FVIII activity will be excluded from analysis if obtained within 72 hours (or 3 calendar days if time is not available) since the last infusion of exogenous FVIII replacement therapy.

The second-ranked secondary efficacy endpoint is:

- The change from baseline (prior to BMN 270 infusion while receiving FVIII prophylaxis) in the annualized utilization (IU/kg/year) of exogenous FVIII replacement therapy in the efficacy evaluation period ("Post FVIII Prophylaxis to Last Visit")

The annualized utilization (IU/kg/year) of exogenous FVIII replacement therapy is defined as

$$\frac{\text{Sum of FVIII use (IU/kg) during calculation period}}{\text{Total number of days during the calculation period}} \times 365.25$$

The primary analyses for the annualized utilization (IU/kg/year) of exogenous FVIII replacement therapy will be performed on the Study 270-902 rollover subjects.

The calculation period in these formulas for the post-baseline value is:

- For the primary analysis, the efficacy evaluation period ("Post FVIII Prophylaxis to Last Visit") as defined in Section 13.1.
- For the supportive analyses, the efficacy periods as defined in Section 13.1.

The calculation period for the baseline value is defined in the following:

- For the primary analysis, the calculation period is approximately 6 months in the non-interventional study 270-902; i.e., the baseline values will be derived from the prospectively collected 6-month data in 270-902 up until the BMN 270 infusion date in 270-301.

Study 270-301 Statistical Analysis Plan

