13.3.3 Sensitivity Analysis Methods for Secondary Efficacy Endpoints

A one-sample t-test of the change from baseline to Week 104 in FVIII activity using observed cases will be performed as a sensitivity analysis.

The primary analysis for the change from baseline to Week 104 in FVIII activity using LOCF approach will be performed. Similarly, the primary analysis with imputing missing data at Week 104 to be 0 IU/dL will be performed.

The primary analysis for the change from baseline to Week 104 in FVIII activity will be conducted for the PP population when applicable.

To investigate the robustness of the primary analysis, which uses the median FVIII activity value if more than one assessment falls within an analysis window, a sensitivity analysis may be performed using the mean of the multiple assessments. This sensitivity analysis will be based on the mITT population with the same imputation strategy as the primary analysis.

A mixed model for repeated measures (MMRM) approach will also be used on the observed cases on the mITT population as an alternative approach to evaluate the impact of missing data assuming missing at random. The model will include visit (every 4 weeks, from baseline to Week 104) as the only factor and will use an unstructured covariance matrix. The least squares (LS) mean change from baseline to Week 104 will be reported.

The following sensitivity analyses for the change from baseline in the annualized utilization (IU/kg/year) of exogenous FVIII replacement therapy will be performed:

- The primary analysis will be performed on the PP population when applicable.
- The primary analysis will be performed with baseline (prior to BMN 270 infusion while receiving FVIII prophylaxis) values calculated using the data 12-months prior to study enrollment

The Haemo-QoL-A Total score will be analyzed using an MMRM approach. The model will include visit (baseline, Week 4, Week 12, Week 26, Week 52, Week 76, Week 104) as the only factor and will use an unstructured covariance matrix. The LS mean change from baseline to Week 104 will be reported.

The analyses for Haemo-QoL-A domain scores (Physical functioning, Consequence of bleeding, Role functioning) will be the same as the Total score analyses.

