13.3.5 Joint Analysis of ABR and Exogenous FVIII/Emicizumab Use

Per the study protocol, subjects will discontinue their regular prophylactic FVIII treatment regimen starting Week 5 post the day of BMN 270 infusion and switch to an episodic treatment schedule. In addition, subjects who experience recurrent bleeding episodes may resume their prior FVIII prophylaxis or start prophylactic emicizumab treatment. Because ABR and exogenous FVIII/emicizumab use are not independent, the following analyses will be performed to jointly assess ABR and exogenous FVIII/emicizumab use:

- Paired analysis of ABR and exogenous FVIII/emicizumab use in each of the efficacy evaluation periods defined in Section 13.1. This analysis enables the interpretation of ABR in the context of exogenous FVIII/emicizumab use.
- Summary of ABR in subgroups of subjects determined by the level of exogenous FVIII/emicizumab use:
 - Subjects who did not resume exogenous FVIII/emicizumab prophylaxis
 - Subjects with zero FVIII infusions
 - Subjects with at least one FVIII infusion
 - Subjects who resumed FVIII/emicizumab prophylaxis
 - Subjects who resumed FVIII prophylaxis
 - Subjects who resumed emicizumab prophylaxis

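### The primary FVIII-utilization analysis scores time on emicizumab as zero use, and no utilization sensitivity analysis counts that switch as a failure

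*SAP*

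**What the plan says.** - **Formula.** Section 13.3 defines utilization as "Sum of FVIII use (IU/kg) during calculation period", divided by the days in the period and multiplied by 365.25. In Section 13.7 it is the third hypothesis tested, after ABR non-inferiority and FVIII activity.
- **Period.** For the primary analysis, Section 13.1 runs the period "until subjects complete the study, reach the last visit by data cutoff for the analysis, or withdraw from the study (ETV), whichever is the earliest". Starting emicizumab does not end it.
- **Rescue.** Section 13.2.1 lists the rescue therapy for BMN 270 as FVIII infusions for several purposes "and the emicizumab prophylaxis for hemophilia A". Section 13.3.5 states that "subjects who experience recurrent bleeding episodes may resume their prior FVIII prophylaxis or start prophylactic emicizumab treatment".
- **Supportive periods.** Table 13.1.1 is titled "Efficacy Evaluation Periods for Analyses of Primary and Second-Ranked Secondary Efficacy Endpoints", so it covers utilization. Two of its periods stop at restart; one ends at "Last visit by data cut-off or 1 day before restart of prophylactic treatment, whichever is earlier", and the other is also capped at Week 104. The table note defines restart to include starting emicizumab. The Synopsis and Section 13.3.2 commit to analysing the change in utilization in these periods.
- **Sensitivity analyses.** Section 13.3.3 says "The following sensitivity analyses for the change from baseline in the annualized utilization (IU/kg/year) of exogenous FVIII replacement therapy will be performed" and then lists two: the per-protocol population and the 12-month baseline.
- **ABR comparison.** Sensitivity analysis 5 in Table 13.2.4.1 sets the change in treated-bleed ABR to 0 for a subject who restarts FVIII prophylaxis or starts emicizumab.

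**The concern.** Resuming FVIII and starting emicizumab are two responses to the same event: bleeding recurs and the subject goes back to prophylaxis. The SAP treats them alike in its definition of restart and in ABR sensitivity analysis 5. The primary utilization analysis does not. FVIII resumed after failure is counted in full, while time on emicizumab counts as time without use.

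The comparison is of BMN 270 with FVIII prophylaxis, so a fall in FVIII use produced by a second prophylactic drug is credited to the gene therapy. At stake are the size and meaning of the reported reduction in a confirmatory endpoint. The planned analyses give no utilization figure that keeps the FVIII used after resumption and also deals with emicizumab time.

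**Working it through.** **1. The plan's own figure.** Section 4.5 gives n = 110, effect size 0.6, a one-sample t-test, two-sided alpha 0.05 and power of at least 95%. With the noncentral t distribution (109 degrees of freedom, noncentrality 0.6 × √110 = 6.29), power is 99.999%. The stated figure holds.

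**2. Two equal failures under the primary formula.** These inputs are assumed, not from the SAP: baseline 4,000 IU/kg/year, evaluation period Days 33–770, 300 IU/kg/year until failure, failure at Day 420. The period has 738 days: 387 before failure and 351 after.
- Moves to emicizumab and uses no further FVIII: 300 × 387 / 738 = 157 IU/kg/year, a 96% reduction.
- Resumes FVIII at his baseline rate: (300 × 387 + 4,000 × 351) / 738 = 2,060 IU/kg/year, a reduction of about 48%.

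**3. The same two subjects in a period that stops before restart.** Both score 300 IU/kg/year, a 92.5% reduction. The emicizumab days are gone, but so is the FVIII that the second subject used after resuming. His score improves from 2,060 to 300.

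**4. How the score depends on timing.** Assume Days 33–730 (698 days), use at a fraction u of baseline until the switch, and none afterwards. The change is u × (days before switch) / 698 − 1, whatever the baseline level.

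| Emicizumab start | u = 25% | u = 50% |
|---|---|---|
| Day 200 | −94% | −88% |
| Day 365 | −88% | −76% |
| Day 550 | −82% | −63% |
| Change before the switch | −75% | −50% |

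FVIII given for bleeds or procedures after the switch would still count and would raise these scores.

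**5. Effect on the mean over 112 rollover subjects, with the inputs of step 2.** The number of switchers is not in the SAP; 5 and 8 are assumed.

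| Comparison | Per subject, IU/kg/year | 5 subjects | 8 subjects |
|---|---|---|---|
| Dilution alone: (300 − 157) / 112 | 1.3 | 6 (0.2%) | 10 (0.3%) |
| Emicizumab days charged at baseline rate: 4,000 × 351 / 738 / 112 | 17.0 | 85 (2.1%) | 136 (3.4%) |
| Change set to 0: (4,000 − 157) / 112 | 34.3 | 172 (4.3%) | 274 (6.9%) |

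Percentages are of the assumed baseline. The zero-change rule is harsher because it also discards the reduction achieved before the switch.

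**6. Effect on the test.** Set the change to 0 for k of 110 subjects, with q = k/110. In SD units the mean becomes 0.6(1 − q), and the variance becomes (1 − q)(1 + 0.6²) − [0.6(1 − q)]². The effect size is 0.581 at k = 5, 0.559 at k = 11, 0.518 at k = 22 and 0.477 at k = 33. Power is still above 99.8% at k = 33.

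**The case against.** The endpoint measures what its name says. The objective concerns exogenous FVIII, the unit is IU/kg/year, and emicizumab has no value in that unit. Following subjects to the last visit is a legitimate choice, and preferring a failure imputation to truncation is a choice of estimand. This stands: the formula is not an error. It does not explain why a switch to another prophylactic drug should count fully in favour of BMN 270 without a check beside it.

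A reader might go further in four ways that the SAP does not support.
- *Nothing planned deals with emicizumab time.* The supportive t-tests in the two periods that stop before restart do remove it. Section 13.3.5 pairs ABR with FVIII and emicizumab use, and Section 13.3.8 analyses time to restart.
- *A switcher scores as almost free of FVIII.* That depends on timing and prior use; step 4 runs from −63% to −94%.
- *The ABR analyses treat the two failures in opposite ways.* Sensitivity analysis 5 treats them identically. The Note to File's additional analyses, introduced by "The following sensitivity analyses will be performed by counting exogenous FVIII product use in EEP as bleeding events", are expressly about FVIII product.
- *The Note to File analyses should be rewritten.* The note is dated March 2023 and records what was reported in a CSR submitted in September 2022.

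It is also fair to say that dilution alone is tiny in the step 2 example. The larger shifts in step 5 come from deciding how to charge the failure.

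**Conclusion.** The point holds as a gap in the sensitivity analyses for utilization. The primary analysis favours a failure who moves to emicizumab over an equal failure who resumes FVIII. The truncated periods leave the failure uncounted for both, and nothing in Section 13.3.3 does for utilization what analysis 5 does for ABR.

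Compared with counting the switch as failure, the reported reduction errs in one direction, towards BMN 270. On the assumed inputs the shift in the mean is about 2% to 3% of baseline for 5 to 8 switchers charged at their baseline rate, and 4% to 7% under the harsher zero-change rule. These sizes rest on an assumed baseline, switch day, prior use and number of switchers. The power of the superiority test is not in question, and the Note to File reports that all SAP-specified tests were significant. This is a cheap improvement that bears on the estimate and its interpretation.

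**What to change.** Add one sensitivity analysis of FVIII utilization to Section 13.3.3, for subjects who start emicizumab prophylaxis as defined in the note to Table 13.1.1. Either rule would serve:
- set the change in utilization to 0, mirroring ABR sensitivity analysis 5; or
- charge each day on emicizumab at the subject's own baseline FVIII rate and add the FVIII actually used.

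The second rule puts the switcher level with an equal failure who resumes FVIII at his baseline rate. The first is simpler and more severe. Report the result beside the primary estimate, with the number of emicizumab starters. The 2-year analysis was run in January 2022, so for those data the result should be labelled as added after the findings were known.

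The cost is a few lines of text, one table and a slightly smaller reported reduction. The inputs are FVIII use and emicizumab dates that the SAP's existing analyses already require.

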13.3.1 Primary Analysis Method for Secondary Efficacy Endpoints

If the hypothesis testing for the primary endpoint is significant, the secondary endpoints will be tested sequentially according to the order described above in Section 13.3.

The change from baseline in the FVIII activity at Week 104 post-BMN 270 infusion will be tested using a one-sample t-test. The hypotheses are:

H_0 (null hypothesis): Change = 0 versus H_1 (alternative hypothesis): Change \neq 0.

Only positive changes represent efficacy.

The primary analysis will be based on the mITT population. If any subject in the mITT population has no assessment available at Week 104, the imputation methods specified in Section 5.6 will be used to impute the missing value. Specifically, if the subject discontinues from the study prior to Week 104, the missing value will be imputed to be 0 IU/dL at Week 104; if the subject continues on study, the missing value will be imputed to be the smaller of the median value in the subject's last visit window prior to Week 104 containing a valid observation and the median value in the subject's next visit window post Week 104 containing a valid observation. In the cases where the value of next 4-week window is unavailable (eg. Week 104 is the last visit by the data cutoff date), the missing value will be imputed through linear extrapolation using the median values in last two 4-week windows prior to Week 104 containing a valid observation.

A listing of subjects with no assessment available during Week 104 will be provided, including the imputed value and associated visit window as well as the next available FVIII activity value after Week 104 and associated visit window, if available. This is to assess potential bias in missing data imputation.

The hypotheses for change in the annualized FVIII utilization are:

H_0 (null hypothesis): Change = 0 versus H_1 (alternative hypothesis): Change \neq 0.

Only negative changes represent efficacy. The test of annualized FVIII utilization will use a one-sample t-test with sample variance at a two-sided significance level determined by the fallback procedure. The details are described in Section 13.7.

The hypotheses for change from baseline in ABR for all bleeds are:

H_0 (null hypothesis): Change \geq 0 versus H_1 (alternative hypothesis): Change $<$ 0

The primary analysis for change from baseline in ABR for treated bleeds will be similar as that for change from baseline in ABR for all bleeds.

Study 270-301 Statistical Analysis Plan

The change from baseline in the Haemo-QoL-A Total score at Week 104 post-BMN 270 infusion will be tested using a one-sample t-test on the mITT population using observed cases. The hypotheses are:

H_0 (null hypothesis): Change = 0 versus H_1 (alternative hypothesis): Change \neq 0.

Only positive changes represent efficacy.

The primary analysis for Haemo-QoL-A domain scores (Physical functioning, Consequence of bleeding, Role functioning) will be the same as the Total score analyses.

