5.6 Handling of Dropouts and Missing Data

If a subject withdraws from the study prematurely, the subject will be asked to complete an Early Termination Visit (ETV), the data from which will be included in summaries and analyses.

Missing dates or partially missing dates will be imputed conservatively for concomitant medications and adverse events (AEs) to ensure that an AE is considered treatment emergent when possible and the duration is the longest possible duration.

FVIII activity levels below the lower limit of quantitation (LLOQ) will be imputed as 0 IU/dL. To reduce variation caused by random fluctuation, FVIII activity will be analyzed as the median of observed values in the visit windows as defined in Section 20.1. Missing FVIII activity values will be imputed as follows:

- Dropout missing
For subjects who discontinue from the study early, missing FVIII activity values post-discontinuation will be imputed to be 0 IU/dL through the data cutoff date for the analysis.
- Intermittent missing
For subjects who continue on study, missing FVIII activity values (eg, due to a missed study visit) will be imputed to be the smaller of the last prior non-missing value and the next non-missing value. In rare cases where the next value is unavailable for a subject who did not drop out, the missing value will be imputed through linear extrapolation using the last two prior non-missing values.

Study 270-301 Statistical Analysis Plan

Other missing data imputation for the primary efficacy endpoint and the secondary efficacy endpoints are specified in the corresponding analysis sections.

Other missing data will not be imputed unless otherwise stated.

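### The SAP does not fix the Week 104 FVIII-activity value for subjects who resume FVIII prophylaxis and stay on study, and the rule they most naturally fall under is an unbounded two-point extrapolation

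*SAP*

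**What the plan says.** Four sections of the SAP bear on the Week 104 chromogenic FVIII activity, the first-ranked secondary endpoint.

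- **Section 13.1** ends the primary evaluation period at the earliest of several events. One is withdrawal, for which "FVIII activities post withdrawal will be imputed to be 0 IU/dL through the data cutoff date for the analysis". Another is that subjects "or resume routine FVIII prophylaxis (should that occur) (Restart of FVIII prophylaxis" is then defined. No value is attached to that second event.
- **Section 13.3** takes the Week 104 value as the median within the Appendix 20.1 window (Days 715 to 743). It drops samples taken within 72 hours of an exogenous FVIII infusion and does not repeat the cut at resumption.
- **Section 13.3.1** sets three rules for a missing Week 104 value. For leavers, "if the subject discontinues from the study prior to Week 104, the missing value will be imputed to be 0 IU/dL at Week 104". For the others, "if the subject continues on study, the missing value will be imputed to be the smaller of the median value" before and the one after. Where there is no value after, "the missing value will be imputed through linear extrapolation using the median values in last two 4-week windows prior to Week 104" that hold a valid observation.
- **Section 5.6** gives the general form of the third rule and introduces it with "In rare cases where the next value is unavailable for a subject who did not drop out".

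Section 13.3.5 says who may resume: "subjects who experience recurrent bleeding episodes may resume their prior FVIII prophylaxis or start prophylactic emicizumab treatment".

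**The concern.** Neither imputation section names the subject who resumes FVIII prophylaxis before Week 104 and remains in follow-up. If the Section 13.1 cut applies, this subject has no usable value at Week 104 or later. The zero rule does not apply because the subject has not left the study, and the smaller-of-two rule cannot operate because there is no next value. Only extrapolation is left. It was apparently written for a short gap at the data cut-off, but here it can run over many months.

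A line through two adjacent window medians, projected far ahead, mostly reflects the noise between those two medians. It can produce a negative activity, which is impossible, or credit the product with expression that nobody observed. Both would enter the primary estimate of the first-ranked secondary endpoint and inflate its variance. Section 5.6 imputation also feeds the milestone summaries in Section 13.3.2. By contrast, the example in that section gives a subject lost at Week 60 a value of 0 through Week 104.

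**Working it through.** **Inputs from the SAP.** Nominal visit days (Appendix 20.1): Week 56 = 393, Week 60 = 421, Week 72 = 505, Week 76 = 533, Week 84 = 589, Week 100 = 701, Week 104 = 730. The mITT population is 134 treated less 2 HIV-positive = 132 (Section 4.2). Power statement (Section 4.5): N = 130, effect size 0.6, two-sided 0.05, at least 95%.

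**Assumptions.** The SAP gives no subject-level values and no count of resumers. The window medians, a window SD of 3 IU/dL and 4 to 13 affected subjects are assumed.

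**1. The plan's own figure.** One-sample t-test, df = 129, noncentrality 0.6 × √130 = 6.84. Power is 0.9999993, so the stated figure of at least 95% reproduces.

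**2. The rule as written.** With medians y1, y2 on days d1, d2:

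y104 = y2 + (y2 − y1) × (730 − d2)/(d2 − d1)

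Multiplier on the last 4-week change, by last valid window:

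| Last valid window | Multiplier |
|---|---|
| Week 60 | (730 − 421)/28 = 11.04 |
| Week 76 | (730 − 533)/28 = 7.04 |
| Week 84 | (730 − 589)/28 = 5.04 |
| Week 100 | (730 − 701)/28 = 1.04 |

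For the short gap that the rule seems built for, the multiplier is about 1. For an early resumer it is about 11.

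**3. Values produced.**
- Weeks 56/60 = 10, 8: 8 − 2 × 11.04 = −14.1
- Weeks 56/60 = 8, 10: 10 + 2 × 11.04 = 32.1
- Weeks 72/76 = 12, 8: 8 − 4 × 7.04 = −20.1
- Weeks 72/76 = 4, 5: 5 + 1 × 7.04 = 12.0

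From a last median of 5 IU/dL, a fall of more than 5/11.04 = 0.45 (Week 60) or 5/7.04 = 0.71 (Week 76) over the last two windows gives a negative result.

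**4. Error amplification.** With independent window errors, extrapolating h windows multiplies the SD by √((h+1)² + h²). For h = 11 this is √(144 + 121) = 16.3, so an SD of 3 becomes about 49 IU/dL.

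**5. Effect on the mITT mean, relative to imputing 0 (k × value/132).**

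| k | value −14 each | value +32 each |
|---|---|---|
| 4 | −0.4 | +1.0 |
| 13 | −1.4 | +3.2 |

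These are same-direction extremes. If the errors are independent, the SD of the shift is √k × 49/132, which is 0.7 for k = 4 and 1.3 for k = 13.

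**6. With bounds at 0 and the last median.** The falling example becomes 0 (no shift). The rising one becomes 10, a shift of 4 × 10/132 = 0.3 to 13 × 10/132 = 1.0.

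**The case against.** The route to extrapolation is not the only reading. Section 13.3 applies a window and a 72-hour exclusion, and Section 13.3.1 imputes only where no Week 104 assessment is available and refers to Section 5.6, not 13.1. Restart means prophylaxis at least weekly, so samples more than 72 hours after an infusion can exist. This stands as an ambiguity. The cut at resumption nevertheless looks deliberate: Section 13.1 defines a separate supportive period without it, and Section 13.3.2 analyses that period without imputation. The cut is therefore the better reading. The other reading might admit residual exogenous FVIII, and it still leads to extrapolation where infusions leave no eligible sample.

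A reader might infer that every resumer is extrapolated. That is not so. Those who resume after the Week 104 window keep an observed value, those who later leave before Week 104 get 0, and the chromogenic period does not end at the start of emicizumab. The documents give no count, so they do not refute the word rare in Section 5.6.

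A reader might also infer that failures are turned into responders. The SAP's only responder threshold is 40 IU/dL, for the interim analyses, and the rising example above reaches 32. Subjects who resume for recurrent bleeding would more often have falling activity, so negative values are likelier and the rule would then work against the product.

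Finally, observed-case, LOCF, zero-imputation and MMRM sensitivity analyses are planned, with a listing of imputed Week 104 values. An odd value would be seen. That limits the harm but does not repair the primary estimate.

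**Conclusion.** The concern holds as a gap between Sections 5.6, 13.1, 13.3 and 13.3.1, together with an extrapolation rule that has no limits. Under the Section 13.1 cut, subjects who resume FVIII prophylaxis before the Week 104 window and remain on study can receive negative values or expression that was never observed. The mean is distorted by at most about 1 to 3 IU/dL if 4 to 13 of 132 subjects are affected, the last valid window is near Week 60, and all move in the same direction. Those counts and medians are assumptions. The variance is also inflated.

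A reader might infer that the superiority conclusion is at risk. The documents do not support this: the comparison is with an imputed baseline of 1 IU/dL, and power at the planned effect size is close to 1, so a handful of such values is unlikely to change the test. Nor do the documents make 0 IU/dL the only correct value for these subjects. It is one defensible convention. This is a point that should be fixed, not a critical one.

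**What to change.** Reconcile Sections 5.6, 13.1, 13.3 and 13.3.1 with two additions.

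1. State whether chromogenic samples taken after resumption of routine FVIII prophylaxis count towards the Week 104 value, and which analysis value a subject receives who resumed before the window and stayed on study. A value of 0 IU/dL would match the SAP's own convention for dropouts. If another value is chosen, give the reason.
2. Bound every extrapolated value below by 0 and above by the last observed window median. This follows the caution already built into the smaller-of-two rule.

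The cost is a few sentences in the SAP and a small programming change. The reported mean may move in either direction: up where the present rule gives negative values, down where it projects a rise.
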